4.4 Duration of Follow Up

Patients will be followed for 6 weeks after completion of definitive treatment or until removal (or) termination from study, or until death, whichever occurs first. Patients removed from study for unacceptable adverse events will be followed until resolution or stabilization of the adverse event.

Toxicity notations, quality of life information, and disease status will be recorded. If it is not possible to coordinate a follow-up evaluation at 2 ± 1 months, then a follow-up phone call will

be made to the patient by the treating physician, or clinical trials office designee, in lieu of a visit.

4.5 Assignment of interventions

4.5.1 Allocation sequence generation

Separate randomization lists will be produced by a statistician for current smokers as well as for former/ non-smokers with a goal of 1:1 allocation to both treatment arms.

4.5.2 Allocation concealment mechanism

The sequence of the randomization numbers is kept in sealed envelopes independent of the investigators.

4.5.3 Implementation

The Henry Ford Research Pharmacy will label the tablet packages according to the randomization list. Single sealed envelopes containing the participants' randomization code will be located and the Radiation Oncology Clinic.

4.5.4 Unblinding

Blinding of the investigators, outcome assessors, pharmacists, data analysts and trial participants will be maintained throughout the study. Adverse events (AEs) that are considered serious, unexpected and at least possibly related to the medication would have to be unblinded. The study will be unblinded by the trial statistician after the final visit of the primary endpoint assessment.

4.5.5 Withdrawal of participants/stopping rules and urgent safety

Participants have a right to withdraw at any time and may be withdrawn at the investigator's discretion. Reasonable effort should be made to contact any participant lost to follow-up. The information collected before the withdrawal will be included in analysis. Participants will not be replaced. The PI will have the authority to deviate from the protocol if doing so relates to the immediate safety of a participant, where continuing to follow protocol would put that participant at risk. If any of the following criteria are met, study enrolment and study therapy will be suspended: death in any participant, where death is attributed in any way to study therapy or intervention; grade 4 anaphylaxis as defined by the World Allergy Organization (WAO).

Study therapies will be discontinued for any of the following reasons: two or more occurrences of grade 3 or above systemic allergic reactions as defined by the WAO; any AE that presents an unacceptable consequence to the participant; an illness that requires treatment not consistent with protocol requirements; inability to comply with the study protocol and pregnancy.

An internal data safety committee will be formed through the Clinical Trials Office and will meet quarterly to review potential adverse effects from the study medication.

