4.3.3 Adverse Events

Side effects of gabapentin include somnolence, dizziness, peripheral edema, and fatigue. Rarely, patients experience changes in behavior or suicidal ideation. These effects will be evaluated on a weekly basis.

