7. PHARMACEUTICAL INFORMATION

7.1 Gabapentin

Please refer to the FDA-approved package insert for additional information.

a. Description – Anticonvulsant, Miscellaneous; GABA Analog

b. Pharmaceutical Data (as taken from UpToDate) –

Absorption: Variable, from proximal small bowel by L-amino transport system; saturable process; dose-dependent

Distribution: $V_d: 58 \pm 6 \text{ L}$; CSF concentrations are ~20% of plasma concentrations

Protein binding: <3%

Metabolism: Not metabolized

Bioavailability: Inversely proportional to dose due to saturable absorption:

Immediate release:

900 mg/day: 60%

1,200 mg/day: 47%

2,400 mg/day: 34%

3,600 mg/day: 33%

4,800 mg/day: 27%

Half-life elimination:

Adults, normal: 5 to 7 hours; increased half-life with decreased renal function; anuric adult patients: 132 hours; adults during hemodialysis: 3.8 hours

Time to peak: Adults: 2 to 4 hours.

Excretion: Proportional to renal function; urine (as unchanged drug)

Clearance: Apparent oral clearance is directly proportional to CrCl.

c. Administration – Orally

d. Storage and Stability - : Store vials at room temperature and protect from light.

e. Supplier – Gabapentin is commercially available.

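### The only allergy-specific discontinuation rule in section 4.5.5 needs two grade 3 or above reactions and states no counting level, so a first grade 3 reaction triggers no automatic stop

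*Combined protocol and SAP*

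**What the plan says.** Section 4.5.5 has two tiers of rules.

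- **Suspension of enrolment and study therapy.** The triggers are a death attributed in any way to study therapy, or one case of WAO grade 4 anaphylaxis.
- **Discontinuation.** The list opens with "Study therapies will be discontinued for any of the following reasons". Its first item is "two or more occurrences of grade 3 or above systemic allergic reactions as defined by the WAO" and its second is "any AE that presents an unacceptable consequence to the participant". The rest are an illness whose treatment conflicts with the protocol, inability to comply, and pregnancy.

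The same section lets the investigator withdraw a participant at discretion and adds "The PI will have the authority to deviate from the protocol if doing so relates to the immediate safety of a participant". It also sets up an internal data safety committee that meets quarterly.

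Section 5.1.1 deals with intolerance. The dose may be lowered in 300 mg steps, and the drug should be stopped if intolerance persists. These participants are still followed for the intent-to-treat analysis.

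**The concern.** An investigator who looks up what to do after a grade 3 systemic allergic reaction finds one specific number, and it is two. The rule does not say two of what: two reactions in one person, or two anywhere in the trial. These are different rules. The first governs one participant's dosing. The second is a trial-level signal and says nothing about the person who has just reacted.

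What is at stake is a possible second reaction to a drug the participant does not need for cancer control. The study drug is blinded supportive treatment. Chemoradiation and standard supportive care go on without it, so little is lost by stopping after one reaction. A default stop would be the safer design.

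**Working it through.** The plan states no calculated figure for this rule, so there is nothing to reproduce. The check is a reading of the text, followed by the cost of the fix.

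**1. What each 4.5.5 rule does at a first grade 3 reaction**

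| Rule | Trigger | Met by one grade 3 reaction? |
|---|---|---|
| Suspension, allergy item | one grade 4 anaphylaxis | No |
| Discontinuation, allergy item, counted per participant | two grade 3 or above in that person | No |
| Discontinuation, allergy item, counted across the trial | two grade 3 or above in total | No, if it is the trial's first |
| Discontinuation, unacceptable-AE item | one event judged unacceptable | Only if so judged; then mandatory |
| Investigator withdrawal | discretion | Permitted, not required |
| PI safety authority | immediate safety | Permitted, not required |

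Per participant, the allergy item applies at the 2nd reaction instead of the 1st, a difference of 2 − 1 = 1 reaction. That figure belongs to the per-participant reading only. On the trial-level reading, the individual has no allergy-specific rule below grade 4.

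**2. Which counting level is meant?** Illness, inability to comply and pregnancy are all events in one person, and trial-level suspension has its own sentence. Both facts favour the per-participant reading. Neither settles it, because the section heading speaks of stopping rules and the item carries no qualifier.

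**3. Does another section supply an automatic stop?**

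- 2.2.3 excludes known gabapentin hypersensitivity, at entry only.
- 4.3.3 says of the listed side effects, "These effects will be evaluated on a weekly basis". That is monitoring.
- 4.4 says "Patients removed from study for unacceptable adverse events will be followed until resolution or stabilization of the adverse event". It presupposes removal without defining what is unacceptable.
- 4.5.4 governs unblinding, not dosing.
- 5.1.1 starts with dose reduction and makes no exception for allergic reactions.
- 7.1 says "Please refer to the FDA-approved package insert for additional information". The insert is not among the documents, so what it says on hypersensitivity during dosing cannot be checked.

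None of them does in the visible text.

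**4. How far apart are the two counting levels?** The documents give no reaction rate, so this is an illustration with an assumed per-person probability p and 30 participants on gabapentin (half of 60).

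P(at least one reactor) = 1 − (1 − p)^30

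P(at least two reactors) = 1 − (1 − p)^30 − 30p(1 − p)^29

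| Assumed p | At least one | At least two |
|---|---|---|
| 0.1% | 3.0% | 0.04% |
| 1% | 26.0% | 3.6% |
| 5% | 78.5% | 44.6% |

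At p = 1%, the chance of exactly one reactor is 26.0% − 3.6% = 22.4%. In those trials a trial-level count of reactors never reaches two.

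**5. Cost of the fix.** Inputs from 9.1.2: N = 60, a 16% reduction in PROMS at week 7, alpha 0.05, power 80%, dropout 10%. Assumptions: two-sided two-sample t-test, 1:1 arms, and one gabapentin participant who stops at once, gains nothing and stays in the analysis. The plan gives no SD, so the standardized effect d is back-solved from 80% power. Noncentrality is d√(n/2).

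- **n = 30 per arm:** d = 0.736, noncentrality 2.85. Diluted effect 16% × 29/30 = 15.5%; d = 0.711, noncentrality 2.75, power 77.3%.
- **n = 27 per arm** (60 × 0.9 / 2): d = 0.777, noncentrality 2.85. Diluted effect 16% × 26/27 = 15.4%; d = 0.748, noncentrality 2.75, power 77.0%.

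A placebo participant who stops causes no dilution.

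**The case against.** The strongest reply is that the discontinuation list already covers a first reaction. Its second item needs no count and no grade, and once an event is judged to meet it, discontinuation is mandatory. Investigator withdrawal, the PI's authority and the intolerance rule in 5.1.1 add further routes. Quarterly committee review and IRB reporting of qualifying SAEs add oversight, though neither acts at once. All of this stands. It rules out saying that a first grade 3 reaction meets no named stop.

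A reader might also infer that the protocol keeps a participant on drug after one reaction because the specific count is two. The text does not support that. The list says when therapy must stop, and no section says that dosing continues or resumes.

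It is also fair that the WAO grades are not defined in the documents, so the argument cannot rest on a particular clinical description of grade 3, and that the proposed rule keeps a judgement about cause.

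What remains is narrower. The general clause works only after someone makes a judgement, while the same sentence sets a specific count of two for exactly this kind of event. If every first reaction were caught by the general clause, the two-reaction item would do no work at participant level.

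**Conclusion.** The point holds as a minor safety improvement. The allergy item has no counting level, and on either reading a first grade 3 reaction triggers no automatic, allergy-specific stop for that participant. It does not show that such a participant would stay on drug, or that the protocol lacks any means of stopping.

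The frequency cannot be computed from the documents, and the event is assumed to be rare. No endpoint, test or sample size depends on the rule. The conclusion is limited to the visible text, since the package insert and the WAO definitions are not available.

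**What to change.** In section 4.5.5:

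- Require permanent discontinuation of blinded study drug in any participant after the first WAO grade 3 or above systemic allergic reaction not clearly due to another cause.
- State that the dose reduction in 5.1.1 does not apply to such reactions.
- Put any trial-level count that prompts suspension or committee review in a separate sentence, labelled as such.
- Confirm that the participant stays in follow-up for intent-to-treat, as 5.1.1 already provides for intolerance.

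This takes a few sentences in an amendment and changes no visit, analysis or sample size. The downside is that an occasional participant stops study drug for a reaction that occurred on placebo or was due to chemotherapy. Each is 1 of 60 (1.7%) overall, or 1 of 30 (3.3%) in an arm. The fall to about 77% power is an upper bound per gabapentin participant. The real cost is smaller, because such a participant could well have been stopped under the existing judgement clauses.

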5. DOSING DELAYS/DOSE MODIFICATIONS

This study will utilize the CTCAE (NCI Common Terminology Criteria for Adverse Events) version 4.0 for toxicity and Serious Adverse Event (SAE) reporting.

5.1 General Considerations

5.1.1 Dose Modifications for Gabapentin

If patient cannot tolerate gabapentin at the dose specified in this protocol, dose can be reduced in 300 mg (or 1 pill) decrements until side effects subside. If intolerance continues, therapy should be discontinued. Patients who are unable to tolerate the medication will be withdrawn from the study. Patient should be continued to be followed as specified on the protocol, however, for intent-to-treat analysis purposes.

6. ADVERSE EVENT REPORTING:

This study will utilize the NCI Common Terminology Criteria for Adverse Events (CTCAE) version 4.0 for reporting of adverse events (AEs).

Serious Adverse Events (SAE) and adverse events will be carefully recorded, and SAEs will be reported to Henry Ford Hospital's IRB if they meet the IRB's SAE reporting criteria.

Definition of an AE: Any unfavorable and unintended sign (including an abnormal laboratory finding), symptom, or disease temporally associated with the use of a medical treatment or procedure regardless of whether it is considered related to the medical treatment or procedure (attribution of unrelated, unlikely, possible, probable, or definite).

Definition of an SAE: Any adverse experience occurring during any part of protocol treatment and 30 days after that results in any of the following outcomes:

- Death;
- A life-threatening adverse drug experience;
- Inpatient hospitalization or prolongation of existing hospitalization;
- A persistent or significant disability/incapacity;

- Important medical events that may not result in death, be life threatening, or require hospitalization may be considered an SAE, when, based upon medical judgment, they may jeopardize the patient and may require medical or surgical intervention to prevent one of the outcomes listed in the definition. Any pregnancy, including a male patient's impregnation of his partner, occurring on study must be reported to the IRB as a medically significant event. SAEs (more than 30 days after last treatment) attributed to the protocol treatment (possible, probable, or definite) should be reported to the IRB if the reporting criteria is met.

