2. PATIENT SELECTION

2.1 Conditions for Patient Eligibility:

- 2.1.1 Patients being treated with combination radiation and chemotherapy (definitive) therapy for locally advanced (Stage III and IV) squamous cell carcinoma of the oropharynx.
- 2.1.2 Age ≥ 18 .
- 2.1.3 ECOG performance status 0-1.
- 2.1.4 Patients must provide study specific informed consent prior to study entry and be able to fill out toxicity and quality of life related questionnaires.
- 2.1.5 Patients should be concurrently treated with any of the following chemotherapy regimens: high-dose every three week cisplatin, low dose weekly cisplatin, or weekly carboplatin.

2.2 Conditions for Patient Ineligibility:

- 2.2.1 Patients may not be receiving gabapentin, any other investigational agents, or other anticonvulsants.
- 2.2.2 Patients with metastatic disease are excluded from this clinical trial.
- 2.2.3 Patient with allergies or hypersensitivity to gabapentin.
- 2.2.4 Patients receiving surgery as part of their definitive management.
- 2.2.5 Patients who have received prior chemotherapy or radiation therapy for head and neck cancer.
- 2.2.6 Patients unable to complete the required forms; however, verbal completion is adequate if recorded on the form daily.
- 2.2.7 Uncontrolled serious illness including, but not limited to, ongoing or serious active infection requiring IV antibiotics for over 30 days, symptomatic congestive heart failure, unstable angina pectoris, cardiac arrhythmia other than chronic, stable atrial fibrillation, immunocompromised state, significant hepatic insufficiency, significant hematological disease, and any serious or unstable psychological condition.
- 2.2.8 Patients on any of the following medication that cannot find a suitable substitute during the study period: azelastine, orphenadrine, paraldehyde, thalidomide.
- 2.2.9 Patients with severe renal insufficiency (creatinine clearance of < 60 ml/minute)

2.3 Required laboratory data (to be done at time of enrollement):

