4.3 Protocol Treatment

[figure not shown]

Figure 1: Treatment schema, as described below.

4.3.1 Arm 1

Patients will receive a placebo along the same dosing schedule as the experimental arm (patients randomized to placebo will take the same number of capsules as those assigned to gabapentin).

This will also include standard supportive care for treatment-related pain and mucositis as needed during concurrent chemotherapy and radiation treatment, consisting of the following:

- Viscous lidocaine 2% oral solution
- Oral liquid or solid opioid medications- e.g., morphine, oxycodone. These will be introduced and titrated at the discretion of the treating physician when the patient-reported pain score is ≥ 4 on a 0-10 scale.

4.3.2 Arm 2

Gabapentin will be initiated at a dose of 300 mg to be taken at bedtime of the night prior to the first radiation treatment. During week 1, the dose will be 300 mg three times a day for a total daily dose of 900 mg. Starting week 2, the dose will be 600 mg taken 3 times per day for a total daily dose of 1800 mg. This will continue until one week after the end radiation treatment (week 8). Therapy will then be titrated down to 300 mg three times a day for 1 day, and then discontinued all together. The standard supporting care for treatment-related pain and mucositis described above will also be included.

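### Creatinine clearance below 60 ml/minute bars entry, but no renal value is tied to a study-drug action during weeks 2-8 at 1800 mg/day

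*Combined protocol and SAP*

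**What the plan says.** Entry: section 2.2.9 excludes "Patients with severe renal insufficiency (creatinine clearance of < 60 ml/minute"). Section 2.3 is headed "Required laboratory data (to be done at time of enrollement") and lists creatinine as its only test. In Table 1 creatinine is marked before study therapy. The cells for weekly visits and first follow-up are empty.

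Dosing: section 4.3.2 starts gabapentin at 300 mg on the night before radiation, gives 900 mg/day in week 1 and 1800 mg/day from week 2. It adds "This will continue until one week after the end radiation treatment (week 8"), followed by one taper day.

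Pharmacology: section 7.1 says that the drug is not metabolized and is excreted unchanged in urine. It notes "increased half-life with decreased renal function" and "Clearance: Apparent oral clearance is directly proportional to CrCl". It also points to the package insert for further information.

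Dose changes: for a patient who cannot tolerate the drug, section 5.1.1 says "dose can be reduced in 300 mg (or 1 pill) decrements until side effects subside. If intolerance continues, therapy should be discontinued". Section 4.5.5 lists other reasons to stop study therapy: systemic allergic reactions, an adverse event with consequences judged unacceptable, an illness whose treatment does not fit the protocol, inability to comply, and pregnancy. None is a renal threshold.

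**The concern.** The entry criteria treat renal function as relevant to eligibility, and section 7.1 gives a pharmacological reason why it bears on exposure. After enrolment the protocol neither asks for the value again nor says what to do if it becomes known. A patient whose CrCl drops below 60 can stay on 1800 mg/day while everyone follows the plan as written.

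The stake is patient safety in the gabapentin arm. The one stated dose rule responds to symptoms, and those symptoms are hard to attribute here. Fatigue is listed as a common radiation effect (section 4.2.10). Sedation and impaired psychomotor function are listed as opioid effects (section 1.2.2), and opioids are part of supportive care in both arms (sections 4.3.1 and 4.3.2). Investigators are blinded (section 4.5.4), so one who sees creatinine rise does not know whether the capsules contain gabapentin.

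**Working it through.** The plan states no figure on this point, so there is none to reproduce. The check has four parts.

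**1. Does any provision tie a renal value to a study-drug action on treatment?**

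| Provision | What sets it off | Renal value required? |
|---|---|---|
| 5.1.1 dose reduction, then stop | Intolerance | No |
| 4.3.3 weekly side-effect review; weekly patient-reported dizziness (Appendix III) | Symptoms | No |
| Table 1 weekly CTCAE row with the section 6 definition, "Any unfavorable and unintended sign (including an abnormal laboratory finding") | An abnormal value, if one was drawn | No draw required |
| 4.5.5 unacceptable adverse event | Recognised event and judgement | No |
| 4.5.5 illness needing treatment that does not fit the protocol | Recognised illness and judgement | No |
| 4.5.5 withdrawal at the investigator's discretion; "The PI will have the authority to deviate from the protocol if doing so relates to the immediate safety of a participant" | Judgement | No |
| 7.1 reference to the package insert | Reader consults it; content not in the documents | Cannot be checked |

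No row that can be checked sets a renal action level. In addition, Table 1 has visits weekly during radiation and then at 6 weeks after it. The last full-dose week, after radiation ends, has no scheduled assessment.

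**2. Time at full dose.** Weeks 2 to 8 are 7 weeks, and 7 x 7 = 49 days.

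**3. Exposure at a fixed dose.** Exposure = dose / apparent oral clearance. By section 7.1 that clearance is proportional to CrCl, so exposure relative to CrCl 60 is 60/CrCl. The dose is the same on both sides, so saturable absorption does not disturb the ratio. With illustrative CrCl values:

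- CrCl 50: 60/50 = 1.20
- CrCl 45: 60/45 = 1.33
- CrCl 30: 60/30 = 2.0

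For scale, two eligible patients at CrCl 120 (an illustrative value) and 60 already differ by 120/60 = 2.0-fold. The gap concerns exposure above that range.

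**4. When chemotherapy bloods would supply a value.** Assume a draw before each dose (not stated in the documents), dose 1 on the first radiation day and no delays. Section 4.1 then gives:

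- Cisplatin every 3 weeks, 3 doses: days 1, 22 and 43. Study drug runs to about day 56, so 56 - 43 = 13 days follow the last value.
- Weekly cisplatin or carboplatin, 6 doses: days 1, 8, 15, 22, 29 and 36, leaving 56 - 36 = 20 days.
- The last of 35 fractions, at 5 per week from a Monday, falls on day 47.

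**The case against.** The strongest reply has three parts.

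First, eligibility criteria ordinarily stop binding after entry. ECOG 0-1 does not bind on treatment either, so the mere absence of a carried-over limit is not a defect. That stands as a general rule. It has less force here because section 7.1 links this particular criterion directly to drug exposure.

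Second, Table 1 is weak evidence about monitoring. It lists no chemotherapy safety tests at all, not even blood counts, and section 4.1 leaves chemotherapy to the medical oncologist. Creatinine may well be drawn, and any available abnormal value comes under the weekly CTCAE review. This also stands. A reader might infer that renal function goes unwatched for 49 days, and the documents do not support that. They show only that no value is required by the protocol or linked to study drug.

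Third, the harm cannot be sized. A reader might infer that patients with CrCl 45-59 are overdosed at 1800 mg/day, or that declines will be frequent. The documents give neither a harmful exposure level nor a rate of decline. Nor do they support an inference that the PROMS comparison is biased, since patients who stop drug are still followed for intent-to-treat. The package insert may contain relevant guidance, but section 7.1 cites it for information rather than as a dosing rule, and its content cannot be assessed here.

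The quarterly safety committee does not bear on the point either way. Its stated task is to review adverse effects, not to adjust individual doses.

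**Conclusion.** The point holds in a limited form. The protocol uses CrCl to decide who may receive gabapentin and then ties no renal value to any study-drug action while the drug is given at full dose. The safeguards narrow the gap without closing it.

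The ratios in the working rest on the proportionality in section 7.1 and on hypothetical CrCl values. They show direction and scale, not expected harm. No cause or frequency of decline is assumed. The conclusion concerns the protocol text alone and would matter less if site practice already adjusts study drug on chemotherapy bloods. It is a modest safety improvement that is cheap enough to be worth making.

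**What to change.** 1. In Table 1, record the on-treatment creatinine and CrCl values drawn for chemotherapy (assumed routine), with CrCl calculated as at entry.
2. In section 5.1.1, add a hold-or-reduce rule for when CrCl falls below a stated action level, applied identically to gabapentin and placebo capsules so that nobody needs to be unblinded. The clinical team should set the level and the steps. The default is 60 ml/minute because it is the protocol's own entry limit; the documents do not show that it is the right action level.
3. Record renal decline as its own reason for dose change or stopping, and leave intent-to-treat follow-up unchanged.
4. Optional: one draw at the last radiation visit (about day 47), to give a value within the 13 to 20 days left uncovered by chemotherapy bloods.

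**Cost.** A protocol amendment and one data field. The optional draw adds at most 60 x 1 = 60 samples. If chemotherapy bloods prove not to be routine, draws at weeks 3, 5 and 7 would add at most 60 x 3 = 180.

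**Downside.** Delivered gabapentin dose falls slightly in affected patients. As an illustration, suppose 10% of the arm (3 of 30) were held for half of the 49 days. The arm then loses 0.10 x 0.5 = 5% of its planned dose at 1800 mg/day. If the effect shrank in proportion, with a two-sided 0.05 test (sidedness assumed) and a normal approximation, power would be Phi(0.95 x (1.960 + 0.842) - 1.960) = Phi(0.70) = 0.76, against the planned 0.80. Reducing the dose instead of holding it would cost less.

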4.3.4 Study medication accountability

Patient compliance will be evaluated weekly during clinic visits. Patients are expected to receive 3 doses per day (21 per week), 7 days a week during radiation. Patients who take at least 12 doses a week will be considered compliant. Patients that do not begin gabapentin or require a feeding tube will be followed for the endpoints measured in the protocol for an intent-to-treat analysis.

The investigator is required to maintain adequate records of the disposition of the investigational products. Participants will be asked to return unused tablets at the end of radiation treatment and at first follow-up. The unused tablets will be counted by pharmacy.

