9.2.6 Other Quality of Life Metrics

Patients will be asked to complete the FACT-HN and PRO-CTCAE quality of life forms (see Appendix). The FACT-HN will be assessed at baseline and at the 7-week (final week) of radiation. The PRO-CTCAE will be assessed at baseline and weekly with the PROMS scale.

The change in scores from baseline to the 6-week follow-up timepoint will be used for analysis.

All assessments are summarized in Table 1.

Table 1. Subject assessments.

| Parameters | Prior to Study Therapy | Weekly During Radiation Therapy | At First Follow-up (6-weeks post completion) |
|---|------------------------|---------------------------------|--|
| History and Physical ^a | X | | X |
| Performance status ^a | X | | X |
| Creatinine | X | | |
| PROMS Score ^b | X | X | X |
| HN-PSS Score ^a | X | X | X |
| FACT H&N ^b | X | | X |
| Weight | X | X | X |
| Daily opioid use (in morphine equivalents) ^a | X | X | X |
| Assess if feeding tube has been placed ^a | X | X | X |
| CTCAE and other adverse events ^a | X | X | X |
| PRO-CTCAE questionnaire ^b | X | X | X |

^a Physician or evaluator reported.

^b Patient reported.

REFERENCES

1. Starmer, H.M., et al., *Effect of gabapentin on swallowing during and after chemoradiation for oropharyngeal squamous cell cancer*. Dysphagia, 2014. **29**(3): p. 396-402.
2. Chaturvedi, A.K., et al., *Human papillomavirus and rising oropharyngeal cancer incidence in the United States*. Journal of Clinical Oncology, 2011. **29**(32): p. 4294-4301.
3. Marur, S. and A.A. Forastiere, *Head and neck cancer: changing epidemiology, diagnosis, and treatment*. Mayo Clin Proc, 2008. **83**(4): p. 489-501.
4. Pignon, J.-P., et al., *Meta-analysis of chemotherapy in head and neck cancer (MACH-NC): an update on 93 randomised trials and 17,346 patients*. Radiotherapy and Oncology, 2009. **92**(1): p. 4-14.
5. Trott, A., et al., *TAME: development of a new method for summarising adverse events of cancer treatment by the Radiation Therapy Oncology Group*. Lancet Oncol, 2007. **8**(7): p. 613-24.
6. Moslemi, D., et al., *Management of chemo/radiation-induced oral mucositis in patients with head and neck cancer: A review of the current literature*. Radiother Oncol, 2016. **120**(1): p. 13-20.

7. Epstein, J.B., et al., *Neuropathic and nociceptive pain in head and neck cancer patients receiving radiation therapy*. Head & neck oncology, 2009. **1**(1): p. 1.

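### The primary repeated measures ANOVA of PROMS (9.1.1) has no analysis set or missing-score rule, so the intent-to-treat aim stated elsewhere is not carried into it; the follow-up wording in 5.1.1, 4.4 and 4.5.5 also needs reconciling.

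*Combined protocol and SAP*

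**What the plan says.** **Analysis.** Section 9.1.1 makes PROMS the primary endpoint, measured at baseline, weekly during radiation and 6 weeks after radiation ends. It names repeated measures ANOVA for the difference between arms across the whole study, and t-tests week by week. It does not mention intent-to-treat, an analysis set or missing scores. Nothing else in section 9 supplies these for PROMS; 9.1.2 only assumes 10% dropout.

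**Intent-to-treat elsewhere.** Section 4.3.4 states: "Patients that do not begin gabapentin or require a feeding tube will be followed for the endpoints measured in the protocol", for an intent-to-treat analysis. Section 4.5.5 says that data gathered before a withdrawal will be analysed.

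**Follow-up after intolerance.** Section 5.1.1 first allows dose reduction ("dose can be reduced in 300 mg (or 1 pill) decrements until side effects subside"). It then says "Patients who are unable to tolerate the medication will be withdrawn from the study", and immediately adds: "Patient should be continued to be followed as specified on the protocol, however, for intent-to-treat analysis purposes". Section 4.4 runs follow-up for 6 weeks after treatment or "until removal (or) termination from study, or until death, whichever occurs first". It adds "Patients removed from study for unacceptable adverse events will be followed until resolution or stabilization of the adverse event" and "Toxicity notations, quality of life information, and disease status will be recorded", but names neither PROMS nor a schedule for removed patients. Table 1 lists PROMS before therapy, under "Weekly During Radiation Therapy" and at first follow-up, so the schedule follows radiation and not drug intake. Section 4.5.5 permits investigator-decided withdrawal without saying whether drug or assessments stop.

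**The concern.** A repeated measures ANOVA in its classical form needs a score at every visit. With nine planned PROMS visits, one gap removes the patient and all of that patient's other scores. This would work against the intent-to-treat aim and, for patients who withdraw, against the inclusion statement in 4.5.5. Because 9.1.1 is silent, the choice would be made once data are in hand.

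The follow-up wording adds to the exposure. If staff apply 4.4 to one intolerant patient and 5.1.1 to another, collection differs between patients for reasons unrelated to the design, and scores not collected cannot be recovered. Patients who stop for intolerance may differ from those who continue, so losing them can weaken the randomised comparison. The documents do not allow the frequency of stopping, or the size and direction of any bias, to be derived.

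**Working it through.** **1. Wording, side by side.**

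| Question | Section | Answer |
|---|---|---|
| Intolerant patient still followed? | 5.1.1 | Yes, for intent-to-treat |
| | 4.4 | Literally no: follow-up ends at removal, apart from following the adverse event |
| Patient who never starts drug, or needs a feeding tube? | 4.3.4 | Followed for the endpoints |
| Pre-withdrawal data used? | 4.5.5 | Yes |
| Post-withdrawal data used? | 4.5.5 | Not stated |
| Who enters the ANOVA, and how are gaps handled? | 9.1.1 | Not stated |

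The intent is visible in three sections and absent from the one that defines the analysis.

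**2. The plan's own figure.** Section 9.1.2 gives 60 patients, alpha 0.05, 80% power, 10% dropout and a 16% lower PROMS at week 7. It gives no mean, SD or sidedness, so 60 cannot be reproduced forward. Solving backwards: 60 × 0.9 = 54 evaluable, 27 per arm. A two-sided two-sample t-test with 80% power at 27 per arm implies a standardised difference d = 0.777. This d is used below.

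**3. Base case.** If loss is the planned 10% and nobody else misses a visit, 54 patients are complete and proxy power is 80%. There is no shortfall against plan.

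**4. Scattered missed visits (assumed rates).** Inputs: complete baselines; 8 post-baseline visits (7 weekly plus the 6-week follow-up); a proportion m missing per visit. If all 60 patients had every visit there would be 60 × 8 = 480 post-baseline scores.

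- Independent missingness: complete fraction f = (1 − m)^8.
- Clustered missingness (beta-binomial, assumed correlation ρ = 0.3): with s = 1/ρ − 1 and b = (1 − m)s, f is the product over j = 0 to 7 of (b + j)/(s + j).
- Scores collected = 480(1 − m); kept by a complete-case analysis = 480f.
- Proxy power: two-sample t-test at d = 0.777 with 30f per arm, unrounded.

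| m | Pattern | f | Complete of 60 | Scores collected | Discarded | Proxy power |
|---|---|---|---|---|---|---|
| 2% | independent | 0.851 | 51.0 | 470.4 | 62.0 (13%) | 78% |
| 5% | independent | 0.663 | 39.8 | 456.0 | 137.6 (30%) | 67% |
| 10% | independent | 0.430 | 25.8 | 432.0 | 225.4 (52%) | 47% |
| 2% | clustered | 0.925 | 55.5 | 470.4 | 26.6 (6%) | 81% |
| 5% | clustered | 0.821 | 49.2 | 456.0 | 62.1 (14%) | 76% |
| 10% | clustered | 0.669 | 40.2 | 432.0 | 110.8 (26%) | 67% |

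A mixed model on the same data discards none of the collected scores.

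**5. Break-even with the 10% allowance.** Setting f = 0.9: independent, m = 1 − 0.9^(1/8) = 1.3% per visit; clustered, 2.7% per visit.

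**6. Week 7 alone.** A weekly t-test needs only that week's score, so 60(1 − m) = 58.8, 57.0 or 54.0 patients enter and power is 83%, 82% or 80%. The exposure is in the ANOVA across all visits, not in the week-7 comparison on which the trial is sized.

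**The case against.** The strongest reply is that 5.1.1 answers itself. Its follow-up sentence is an explicit exception, so withdrawal there reads most naturally as coming off drug, and a specific rule would normally govern the general wording of 4.4. Table 1 then supplies a PROMS schedule, and the adverse-event sentence in 4.4 may be a safety duty rather than a cap on PROMS. Most of this stands. A reader who saw only the withdrawal sentence might infer that the plan removes intolerant patients from follow-up and analysis; the documents do not support that. What remains is a literal conflict with 4.4 and the failure of 4.5.5 to separate drug from assessments.

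Second, a reader might infer that the plan prescribes a complete-case analysis. It does not: no such rule is written, and the form of ANOVA is not stated. The harm is conditional on the classical form being run by default. Moreover, 4.5.5 covers only data from before a withdrawal, not gaps in patients who stay, and it would be partly honoured by the weekly t-tests.

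Third, the power figures rest on assumed missingness, an assumed correlation and a t-test stand-in for the ANOVA. They model scattered missed visits, not stopping for intolerance as such. This stands in full; they do not show that the trial is underpowered. The protocol also calls gabapentin generally well tolerated, and stopping may be uncommon.

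Fourth, one sentence on the analysis set and missing scores would close the gap, and a mixed model is not the only option. That is fair. It is preferred because it tests the same contrast on the same data and uses every observed score.

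**Conclusion.** The point holds and should be fixed. The firm part is textual: 9.1.1 states neither who is analysed nor what happens to missing PROMS scores, and the named method in its classical form would defeat aims stated in 4.3.4, 5.1.1 and, for withdrawn patients, 4.5.5. The conflict between 5.1.1 and 4.4 is a secondary clarification, since continued follow-up is plainly intended.

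The size is conditional. For 2% to 10% missing per visit, a complete-case ANOVA would keep about 51 down to 26 patients (independent) or about 55 down to 40 (clustered). These rates and the 0.3 correlation are assumptions. At the planned 10% dropout with no other gaps, nothing is lost against plan, and week-7 power stays at about 80% or more in every scenario shown. The power of the ANOVA itself depends on the time course and within-patient correlation, which are not given. A reader might go further and infer a bias for or against gabapentin; nothing in the documents fixes its direction or size.

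**What to change.** 1. **Section 9.1.1.** State that all randomised patients are analysed in the arm to which they were assigned. Replace the ANOVA with a likelihood-based mixed model for repeated measures that uses every observed PROMS score and tests the same arm difference across the whole study period. The model assumes scores are missing at random, so one sensitivity analysis for scores missing after early stopping is a useful option.
2. **Sections 5.1.1, 4.4 and 4.5.5.** Reconcile them so that stopping study drug is distinct from leaving the study, and scheduled PROMS continues after drug is stopped unless the patient withdraws from follow-up or dies. The criteria for stopping drug are neither questioned nor changed.

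The cost is wording in four sections and slightly more analysis work, with no added patients or visits. Patients off drug would keep completing questionnaires at visits they are already expected to attend.
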